3.3.2 Observation indicators

3.3.2.1 Primary Outcomes

Incidence of AKI within 7 days postoperatively

Percentage of subjects who developed new-onset AKI within 7 days postoperatively. AKI diagnosis was determined by clinicians who remained blinded to group assignments, based on the criteria established by the Global Outcomes in Kidney Disease (KDIGO) standards, as specified below (meeting any one criterion suffices):

1) Serum creatinine elevation $\geq 26.5 \mu\text{mol/L}$ within 48 hours; 2) Increase ≥ 1.5 -fold from baseline within 7 days; 3) Urine output reduced to $<0.5 \text{ mL/kg/h}$ for 6 consecutive hours.

Baseline creatinine was defined as the most recent preoperative serum creatinine measurement.

After baseline creatinine levels were obtained, serum creatinine and urine output were measured daily for seven consecutive days postoperatively.

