3.3.3 Statistical Analysis Plan

All data in this study were processed using SPSS 26.0 and R 4.3.0 software.

For continuous variables, the Shapiro-Wilk normality test is first performed. Variables conforming to normal distribution are expressed as "mean \pm standard deviation," with intergroup comparisons conducted using the independent samples t-test. Variables not conforming to normal distribution are represented by median values (25th and 75th percentiles), and intergroup comparisons are performed using the Mann-Whitney U rank-sum test. Categorical variables are presented as frequencies (percentages), with intergroup comparisons analyzed using the χ^2 test. If theoretical frequencies do not meet the test requirements, the Fisher exact probability method must be employed.

The primary endpoint of this study was the incidence of AKI within 7 days postoperatively, analyzed based on the intention-to-treat principle. Kaplan-Meier curves were constructed to plot the cumulative incidence of AKI within 7 days postoperatively for both groups, with intergroup comparisons performed using the log-rank test. The Cox proportional hazards regression model was employed to estimate the hazard ratio (HR) and its 95% confidence interval for the ta-VNS group versus the sham stimulation group. A single-factor COX regression model incorporating only grouping variables was first fitted to estimate the crude effect, followed by a multivariate

COX regression model that adjusted for preoperative eGFR (<90 vs. ≥ 90 mL/min/1.73 m²), diabetes history (present vs. absent), left ventricular ejection fraction (<35% vs. $\geq 35\%$), and surgical type (high-risk group [valve and coronary artery combined/aortic surgery] vs. low-risk group [valve and septal repair]) as covariates. Under the random missingness assumption, imputation models were constructed based on covariates related to outcomes and missingness states, generating 20 imputed datasets for analysis, with results combined according to the Rubin rule. Under the non-random missingness assumption (all missing values in the ta-VNS group were AKI, while all missing values in the sham stimulation group were non-AKI), intergroup comparisons were re-evaluated.

The severity of AKI was analyzed using multivariate ordered logistic regression, adjusting for the same covariates as in the primary analysis and testing the proportional hazards assumption. Results were reported as odds ratios (OR) and their 95% confidence intervals (CI).

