Unless otherwise specified, all tests were conducted as two-tailed tests with a significance level set at $\alpha = 0.05$, meaning that differences were considered statistically significant when $P < 0.05$.

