3.4 Research Flowchart

IV. Sample Size Calculation

The sample size for this study was estimated based on preliminary experimental results from our research center. In the pilot study, the incidence rates of CPB-associated AKI in the ta-VNS group and sham stimulation group were 17.1% and 37.9%, respectively. With a significance level of $\alpha = 0.05$ (bilateral) and a power of $1 - \beta = 0.80$, calculated using G*Power software (version 3.1.9.7), 68 patients were required in each group. Considering a 10% dropout rate, a total of 152 patients were enrolled in this study, with 76 patients in each group.

V. Data Management and Confidentiality

Only investigators authorized by the principal investigator are permitted to access or analyze data. Computer systems used for data management must be password-protected, and paper documentation must be locked.

All information related to the subject's identity is kept confidential, and such information shall not be disclosed beyond the scope permitted by applicable laws and/or regulations.

VI. Informed Consent

Prior to enrollment in this study, the investigator responsible for obtaining informed consent must provide each participant with a comprehensive written explanation regarding the study's objectives, nature, procedures, potential benefits, and risks. Participants should be informed of their right to withdraw from the study at any time. Before enrollment, each participant must be fully informed and given sufficient time to consider participation. Enrollment is permitted only after voluntary participation and signing of the informed consent form.

The vulnerable groups potentially involved in this study include elderly individuals and illiterate persons. If the subject is unable to read or sign the informed consent form due to lack of capacity for action, their guardian must act as proxy for the informed consent process and sign the document. If the subject lacks the ability to read the informed consent form (e.g., illiteracy), a witness must observe the informed consent process and sign the consent form.

VII. Adverse Events and Related Management Measures

ta-VNS is a selective, non-invasive, and low-risk effective VNS strategy. The primary

adverse events include pain, influenza-like symptoms, and local skin discomfort, which resolve immediately after cessation of stimulation. To date, no literature has reported serious adverse events associated with this procedure.

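### The primary endpoint counts 6 consecutive hours of oliguria as AKI, but the only stated schedule for urine output is daily, which cannot exclude or time such an episode

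*Combined protocol and SAP*

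**What the plan says.** Section 3.3.2.1 (Primary Outcomes) defines AKI within 7 days by three KDIGO criteria, two on creatinine and one on urine output, and states that "meeting any one criterion suffices". The urine criterion is output below 0.5 mL/kg/h "for 6 consecutive hours". The section ends with the only statement on collection: "serum creatinine and urine output were measured daily for seven consecutive days postoperatively".

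Section 3.3.2.2, item 1, stages AKI partly by the duration of oliguria: 6 to 12 hours for Stage 1, 12 hours or more for Stage 2, and 24 hours or more at a lower rate for Stage 3. Item 3 defines persistent AKI as still meeting the AKI criteria on day 7.

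Section 3.3.3 (Statistical Analysis Plan) treats the primary endpoint as time to event: "Kaplan-Meier curves were constructed to plot the cumulative incidence of AKI within 7 days postoperatively for both groups", with a log-rank test and Cox models.

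No section names an hourly or 6-hourly interval, a source such as the nursing or ICU chart, a rule for turning a daily volume into a 6-hour rate, or a rule for patients without interval data.

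**The concern.** A criterion that is sufficient alone for the only primary endpoint needs data at a resolution of hours, and the stated schedule gives days. Creatinine and urine output share one sentence and one frequency, so one value per day for each is the natural reading. Followed literally, that schedule lets short oliguric episodes pass unseen. The patient is then counted as AKI-free rather than as missing, so the multiple imputation and the worst-case analysis in section 3.3.3 would not address it.

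Two consequences need to be kept apart. Under-detection that is equal in both arms removes events. Under-detection that depends on where the patient is nursed is more serious. If hourly values happen to exist only in the ICU, a patient who leaves earlier has less opportunity to be counted. ICU stay is a listed outcome (section 3.3.2.2, item 8) that the stimulation might change. A shorter ICU stay in the ta-VNS arm could then look like less AKI.

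**Working it through.** **1. What a daily total can and cannot show.** Inputs: the 0.5 mL/kg/h threshold and the 6-hour and 12-hour durations from sections 3.3.2.1 and 3.3.2.2. The rates below are illustrative. Daily mean = (sum of hours × rate) / 24.

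- 6 h at 0.3, 18 h at 1.0: (1.8 + 18.0)/24 = 0.825. Meets the definition; the daily mean looks normal.
- 6 h at 0, 18 h at 0.7: (0 + 12.6)/24 = 0.525. Also hidden.
- Break-even for 6 h of no output: (24 × 0.5)/18 = 0.67. Any average of 0.67 or more over the other 18 hours hides it.
- Stage 2 example, 12 h at 0.3 and 12 h at 1.0: (3.6 + 12.0)/24 = 0.65. Hidden.
- Conversely, if the daily mean is below 0.5, at least one of the four 6-hour blocks must average below 0.5. A low total therefore does flag oliguria, reading the criterion as a 6-hour average.
- Stage 3 spans 24 hours, so a daily total approximates it apart from the alignment of the window.

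**2. The plan's sample size.** Inputs from section IV: "the incidence rates of CPB-associated AKI in the ta-VNS group and sham stimulation group were 17.1% and 37.9%, respectively", two-sided alpha 0.05, power 0.80; "68 patients were required in each group". Unpooled normal approximation:

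n = (1.960 + 0.842)² × (0.171 × 0.829 + 0.379 × 0.621) / 0.208² = 7.849 × 0.3771 / 0.04326 = 68.4.

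This is 69 when rounded up, against the stated 68. Dropout: 68/0.9 = 75.6, so 76 per group and 152 in total, as stated. The pooled formula gives 72 per group, and power at 68 per group of 0.78. The sample size is not the source of this issue.

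**3. Illustration of size.** Assume that a fraction f of AKI cases qualifies by urine output alone, equal in both arms, and that the rates in section IV reflect full detection. If all these cases are missed, each rate is multiplied by (1 − f). If half are missed, it is multiplied by (1 − f/2). Power at 68 per group, pooled formula:

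| f | all missed | half missed |
|---|---|---|
| 0 | 0.78 | 0.78 |
| 10% | 0.72 | 0.75 |
| 20% | 0.65 | 0.72 |
| 30% | 0.58 | 0.69 |
| 50% | 0.42 | 0.62 |

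**4. Effect measures under equal loss.** With f = 20% and all such cases missed, the rates become 0.8 × 17.1 = 13.7% and 0.8 × 37.9 = 30.3%.

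- Risk ratio: 17.1/37.9 = 0.45 before; 13.7/30.3 = 0.45 after.
- Approximate hazard ratio, ln(1 − p₁)/ln(1 − p₂): 0.39 before; 0.41 after.
- Risk difference: 20.8 points before; 0.8 × 20.8 = 16.6 after.

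Equal loss costs events, absolute difference and power. It leaves the ratio almost where it was.

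**The case against.** A reader might infer that urine output is recorded only once a day, that the 6-hour criterion therefore cannot be applied, and that AKI will be misclassified. The documents do not support that. The text says daily. It does not say one value or a 24-hour total, so hourly bedside charting summarised each day is not excluded. For pain scores, section 3.3.2.2 does state a minimum number of records per day; for urine output it states none. Blinded clinicians make the diagnosis and are not expressly confined to one figure. As shown above, a very low daily total still points to a qualifying block, and Stage 3 is roughly assessable.

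Other limits also stand:

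- Equal under-detection does not bias the risk ratio, and it barely moves the hazard ratio that section 3.3.3 plans to report.
- The dependence on ICU stay is conditional. Nothing says that charting stops at ICU discharge.
- Onset known only to the day is not peculiar to urine output, because creatinine is also measured daily.
- A fixed window read from the ICU chart would not by itself cure the problem, since no section guarantees that every patient stays in the ICU for the whole window.

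These points narrow the concern but do not remove it. On the generous reading, the interval, the source and the period covered are still unstated for a criterion that can decide the primary endpoint alone. Blinding protects judgement; it does not supply values that were not collected.

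**Conclusion.** The stated schedule does not support a stated primary criterion. On the plain reading, AKI that qualifies by urine output alone may be missed, and the split between Stages 1 and 2 and the day-7 persistence rule share the weakness. If finer values exist only in the ICU, detection would depend on a trial outcome and could favour either arm.

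The size cannot be fixed from the documents, because they do not give the share of AKI met by urine output alone. The power range of 0.72 to 0.42 rests on an assumed share of 10% to 50%, complete and equal non-detection, and pilot rates free of the same problem. The protocol does not say how the pilot ascertained AKI. If it used the same daily record, the planning rates already contain the loss, and the power argument weakens. The bias argument does not depend on those rates, but it remains conditional on where charting takes place. It would be wrong to conclude that the endpoint is unusable or that the treatment effect is necessarily diluted.

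**What to change.** In section 3.3.2.1, replace the daily schedule for urine output with hourly, or at most 6-hourly, charted values over one postoperative window. The window should be the same for every patient and lie where such charting is available whether or not the patient has left the ICU. Hourly is preferable, because an episode that straddles two fixed blocks can still be hidden: 3 h at 0.3 and 3 h at 1.0 in each block average (0.9 + 3.0)/6 = 0.65.

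Name the data source, and state how patients without interval data are classified. Apply the urine criterion only in that window and the creatinine criteria for all 7 days, and carry the same rule into staging and persistent AKI. In section 3.3.3, prespecify AKI by creatinine alone over 7 days as the key sensitivity analysis.

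The cost is some chart abstraction, a case report form change and a few lines of SAP text. The real downside is that oliguria outside the window no longer counts, which slightly narrows the 7-day endpoint. The sample size need not change on this account. The change is best made early, since interval values not captured at the time may not be recoverable.

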3.3.2.2 Secondary Outcomes

1) Severity of AKI

Within 7 days postoperatively, the postoperative AKI classification was assessed according to KDIGO criteria based on AKI severity (KDIGO staging: Stage 1/2/3):

Stage 1: Serum creatinine elevation ≥ 0.3 mg/dl or 1.5 – 1.9 times the baseline value, or urine output < 0.5 mL/(kg · h) for 6 – 12 hours;

Stage 2: Serum creatinine levels increased 2.0 – 2.9-fold, or urine output < 0.5 mL/(kg · h) for ≥ 12 hours;

Stage 3: Serum creatinine elevation ≥ 3.0 mg/dl, or ≥ 3 times the baseline value, or urine output < 0.3 mL/(kg · h) for ≥ 24 hours, or requiring RRT.

The AKI severity grading was determined by the highest KDIGO stage achieved within 7 days postoperatively.

2) Renal replacement therapy

The proportion and duration of acute RRT required during hospitalization.

3) Renal function recovery

In patients with AKI, those who still meet AKI criteria on postoperative day 7 were defined as having persistent AKI. The time from diagnosis to the first recovery of serum creatinine to within 1.5 times the baseline level without the need for RRT was calculated as the creatinine recovery time.

4) Long-term renal function

Serum creatinine and eGFR at 30 days postoperatively.

5) Autonomic nervous function

5-minute electrocardiogram (ECG) signals were collected preoperatively and at 24 hours, 48 hours, and 72 hours postoperatively, with heart rate variability (HRV) analyzed using Kubios HRV software.

6) Early recovery quality

Postoperative early recovery quality was systematically evaluated from multiple dimensions. Mechanical ventilation duration was defined as the time from the first successful extubation after surgery. The vasoactive drug index was calculated daily within 7 days postoperatively, with peak values and mean values recorded separately. Delirium incidence was assessed daily using either

the Confusion Assessment Measure (CAM) or the ICU Confusion Assessment Measure (CAM-ICU) for both preoperative and postoperative periods (over 7 consecutive days). Early cognitive function was screened using the Mini-Mental State Examination (MMSE) on preoperative day 1, postoperative day 3, and postoperative day 7. Sleep quality was evaluated using the Richards-Campbell Sleep Questionnaire (RCSQ) on preoperative day 1, postoperative day 1 morning, and postoperative day 3 morning to assess prior night sleep status. Recovery quality was scored using the 15-item Quality of Recovery Scale (QoR-15) on preoperative day 1, postoperative day 1, postoperative day 3, and postoperative day 7. Pain and analgesic demand were recorded as baseline pain levels on preoperative day 1 and pain numerical scores (NRS) within 48 hours postoperatively (recorded at least once daily), along with total opioid consumption within 48 hours postoperatively (converted to oral morphine equivalents).

7) Perioperative complications and mortality rate

The incidence rates of cardiovascular complications (including new-onset atrial fibrillation and other arrhythmias, acute myocardial infarction, postoperative myocardial injury, and low cardiac output syndrome), stroke, pulmonary embolism, pulmonary infection, deep vein thrombosis, surgical site deep infection, and all-cause mortality within 30 days postoperatively.

8) Resource consumption

Length of hospital stay, ICU stay duration, and re-admission rate due to complications.

9) Biomarkers

To comprehensively evaluate patient status and explore the pathogenesis of AKI, this study detected the following biomarkers:

a) Routine testing: Collect daily routine laboratory data before surgery and for 7 days postoperatively, including C-reactive protein (CRP), neutrophil-to-lymphocyte ratio (NLR), cardiac troponin (cTn), creatine kinase isoenzyme MB (CK-MB), N-terminal pro-brain natriuretic peptide (NT-proBNP), and serum cystatin C.

b) Specific inflammatory markers and renal injury indicators: Peripheral blood samples were collected at 24h, 48h, and 72h postoperatively and placed in EDTA anticoagulation tubes. Plasma interleukin-6 (IL-6) and neutrophil gelatinase-associated lipocalin (NGAL) concentrations were detected in batches using the ELISA method.

c) Peripheral blood immune cell phenotype analysis: Peripheral blood samples were collected at 24h, 48h, and 72h postoperatively and placed in EDTA anticoagulation tubes. Peripheral blood mononuclear cells (PBMCs) were isolated within 4 hours. Multicolor flow cytometry was employed to detect the expression level of $\alpha 7$ nAChR on the surface of CD14⁺ monocytes and the proportion of intracellular IL-6⁺, as well as the proportions of Th17 (IL-17A⁺) and Treg (CD25⁺CD127^{low/-}) subsets among CD4⁺ T cells, with the Th17/Treg ratio calculated. The analysis was performed using a CytoFLEX flow cytometer and FlowJo software.

Note: Items b and c represent exploratory additional testing mechanisms. A total of 40 patients were selected from the overall sample using stratified random sampling for additional diagnostic evaluation items. The stratification factors included group assignment and Cleveland Clinic score-predicted risk level of dialysis-dependent AKI.

All samples were processed and analyzed using a blinded method. All blood samples were aliquoted into low adsorption cryovials (0.5 mL/vial) to avoid repeated freeze-thaw cycles, and immediately stored in an ultra-low temperature freezer at -80 ° C. Complete sample numbering and time records were established. Upon study completion, the samples were disposed of in accordance with medical waste disposal standards.

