The proportion of patients requiring RRT during hospitalization was compared between groups using χ^2 test or Fisher's exact probability method; the duration of RRT was compared between groups based on its distribution characteristics using independent samples t-test or Mann-Whitney U test.

The proportion of patients with persistent AKI was compared between groups using the χ^2 test; the time to renal function recovery was plotted as cumulative recovery curves using the Kaplan-Meier method, with intergroup comparisons performed via the log-rank test. Patients who did not recover during the observation period were treated as censored data.

Serum creatinine and eGFR at 30 days postoperatively were compared between groups using independent samples t-test or Mann-Whitney U test based on their distribution characteristics.

HRV was analyzed using generalized estimating equations, with grouping, time points, and their interaction terms included as fixed effects. The optimal working-related matrix structure was selected based on the quasi-likelihood independence criterion. Significant group \times time interaction terms indicated statistically distinct temporal trends in HRV metrics between the two groups.

The duration of mechanical ventilation, peak/mean values of vasoactive drug index, peak/mean values of postoperative 48-hour pain NRS scores, and total opioid consumption were compared between groups using independent samples t-test or Mann-Whitney U test based on

their distribution characteristics. The incidence of delirium was compared between groups using χ^2 test. MMSE, QoR-15, and RCSQ were analyzed using generalized estimating equations (GEE), with model specifications identical to those used for HRV analysis.

The incidence rates of new-onset atrial fibrillation, pulmonary infection, stroke, and 30-day all-cause mortality were compared between groups using χ^2 test or Fisher's exact probability method. If the number of events was sufficient, Cox proportional hazards regression model could be employed for analysis, with adjustment for covariates when necessary. Hazard ratios (HR) and their 95% CI were reported.

Hospitalization duration and ICU stay duration were treated as continuous variables, which were expected to follow a skewed distribution. Between-group comparisons were performed using the Mann-Whitney U test. The re-admission rate due to complications was compared using the χ^2 test.

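### Creatinine recovery time is tested between arms only among patients who develop AKI; persistent AKI, severity and RRT duration lack a stated analysis population, and the severity model is checked for the wrong assumption

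*Combined protocol and SAP*

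**What the plan says.** All references are to the combined protocol and SAP.

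- **Recovery time.** Section 3.3.2.2, item 3, measures it from AKI diagnosis to the first return of creatinine to within 1.5 times baseline without RRT. Section 3.3.3 says "the time to renal function recovery was plotted as cumulative recovery curves using the Kaplan-Meier method", with a log-rank test between groups. Patients who do not recover are censored; no rule is given for death.
- **Persistent AKI.** The same item says "In patients with AKI, those who still meet AKI criteria on postoperative day 7 were defined as having persistent AKI". Section 3.3.3 compares the proportion by chi-square and does not say whether the denominator is AKI patients or all patients.
- **Severity.** Item 1 lists KDIGO stages 1, 2 and 3, with no category for patients without AKI. Section 3.3.3 specifies an ordered logistic model, "adjusting for the same covariates as in the primary analysis and testing the proportional hazards assumption". It names no analysis population.
- **RRT.** Item 2 covers the proportion and duration of RRT in hospital. In section 3.3.3, "the duration of RRT was compared between groups based on its distribution characteristics", by t-test or Mann-Whitney. No value is assigned to patients who never receive RRT.
- **Intention to treat.** Section 3.3.3 states this for the primary endpoint only.

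**The concern.** The hypothesis in section II is that ta-VNS lowers the incidence of AKI. If it does, AKI patients in the two arms are no longer comparable: the active arm's cases are those that treatment failed to prevent. Any comparison within cases then mixes the effect of treatment with the effect of selection.

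For recovery time no other reading is possible, because the clock does not start without AKI. For the other three outcomes the plan leaves the choice open, and with an open denominator the choice can be made after results are seen. Section II names AKI severity and renal function among the aims, so these results will be reported. At stake is a misleading secondary finding in either direction: a real benefit that disappears, or a false signal of harm.

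The model check is a separate, simple error. Ordered logistic regression assumes proportional odds across the cut-points of the scale; proportional hazards belongs to the Cox model.

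**Working it through.** **Inputs from the documents.** Section IV gives the AKI rates: "the incidence rates of CPB-associated AKI in the ta-VNS group and sham stimulation group were 17.1% and 37.9%, respectively". It adds "68 patients were required in each group" and "Considering a 10% dropout rate, a total of 152 patients were enrolled in this study, with 76 patients in each group". Section I gives an RRT rate of 2–3%. The documents give no persistence rate and no split of AKI by stage, so those below are assumptions, shown over a range.

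**Plan's own figure (context only).** Unpooled normal approximation, two-sided 0.05, power 0.80: n = (1.960 + 0.842)² × (0.171 × 0.829 + 0.379 × 0.621) / 0.208² = 68.4 per arm, in line with the stated 68. Then 68 / 0.90 = 75.6, or 76. The sample size is not in dispute here.

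**Size of the AKI-only groups.** 0.171 × 76 = 13.0 and 0.379 × 76 = 28.8, so about 13 versus 29. With 68 evaluable per arm: 11.6 and 25.8, so about 12 versus 26. An AKI-only analysis omits (152 − 41.8) / 152 = 72.5% of randomised patients.

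**Persistent AKI.** Let q be the share of sham AKI that persists and f the true relative cut in persistent cases.

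- AKI-only share: q on sham; q × 0.379 × (1 − f) / 0.171 on ta-VNS.
- All-randomised share: q × 0.379 on sham; q × 0.379 × (1 − f) on ta-VNS.
- Proportional prevention means f = 1 − 0.171/0.379 = 0.549.

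| q | f | AKI-only, sham | AKI-only, ta-VNS | All randomised, sham | All randomised, ta-VNS |
|---|---|---|---|---|---|
| 20% | 0 | 20.0% | 44.3% | 7.6% | 7.6% |
| 20% | 0.25 | 20.0% | 33.2% | 7.6% | 5.7% |
| 20% | 0.549 | 20.0% | 20.0% | 7.6% | 3.4% |
| 30% | 0 | 30.0% | 66.5% | 11.4% | 11.4% |
| 30% | 0.25 | 30.0% | 49.9% | 11.4% | 8.5% |
| 30% | 0.549 | 30.0% | 30.0% | 11.4% | 5.1% |
| 40% | 0 | 40.0% | 88.7% | 15.2% | 15.2% |
| 40% | 0.25 | 40.0% | 66.5% | 15.2% | 11.4% |
| 40% | 0.549 | 40.0% | 40.0% | 15.2% | 6.8% |

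With f = 0 or 0.25 the AKI-only comparison points to harm. With f = 0.549 it shows no difference although persistent AKI has more than halved.

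**Would the false signal reach significance?** Illustrative persistent counts among 13 ta-VNS and 29 sham AKI cases:

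| Persistent, ta-VNS v sham | AKI-only shares | Chi-square P (uncorrected) | Fisher P |
|---|---|---|---|
| 9 v 9 | 69% v 31% | 0.021 | 0.041 |
| 7 v 7 | 54% v 24% | 0.059 | 0.08 |
| 6 v 6 | 46% v 21% | 0.09 | 0.14 |
| 7 v 9 | 54% v 31% | 0.16 | 0.19 |
| 4 v 9 | 31% v 31% | 0.99 | 1.00 |

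Equal counts are no difference at all over 76 per arm. The P values show that a significant false result is possible but not typical.

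**Severity.** Common odds ratio for a worse stage, ta-VNS versus sham, from an ordered logit on expected cell shares. The sham stage splits are assumed.

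| Sham split, stages 1/2/3 | Cut in stages 2–3 | AKI-only, stages 1–3 | All randomised, levels 0–3 |
|---|---|---|---|
| 80/15/5 | 0 | 3.10 | 0.37 |
| 80/15/5 | 25% | 1.97 | 0.36 |
| 80/15/5 | 54.9% | 1.00 | 0.34 |
| 70/20/10 | 0 | 4.08 | 0.39 |
| 70/20/10 | 25% | 2.22 | 0.37 |
| 70/20/10 | 54.9% | 1.00 | 0.34 |
| 60/30/10 | 0 | 7.16 | 0.41 |
| 60/30/10 | 25% | 2.67 | 0.38 |
| 60/30/10 | 54.9% | 1.00 | 0.35 |

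**RRT duration.** 0.02 × 152 = 3.0 and 0.03 × 152 = 4.6, so about 3–5 recipients in the whole trial.

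**The case against.** A reader might infer that all four outcomes are restricted to AKI or RRT patients. The text does not say so. The wording on persistent AKI defines a case, since a patient must have AKI for it to persist, and the chi-square comparison can be read as a proportion of all patients in each arm. Severity and RRT duration have gaps rather than a stated restriction. This objection stands; only recovery time is conditional on every reading.

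A reader might also infer that these analyses would show harm. That needs ta-VNS to prevent mainly mild or transient AKI, on which the documents are silent. Under proportional prevention the benefit is hidden, not reversed, and at these numbers significance is uncertain even when the direction reverses. This stands too.

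Unselected comparisons already exist: the primary endpoint, the proportion needing RRT, 30-day creatinine and eGFR, and 30-day mortality. They would help a reader put an AKI-only result in context. They do not settle which population the open analyses use, and they do not make the recovery-time test a randomised comparison.

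**Conclusion.** The point holds for recovery time without further assumptions: followed as written, the log-rank test compares about 13 with 29 patients selected by the primary endpoint, if the design rates apply. It holds for persistent AKI, severity and RRT duration as a gap in specification. If that gap is filled by analysing cases only, the comparison misleads across the assumed range. The odds ratio for severity would be 1.97–7.16 in AKI cases, against 0.36–0.41 in all randomised patients, when stages 2–3 are cut by 0–25%; it would be 1.00 against 0.34–0.35 under proportional prevention. These sizes rest on assumed persistence shares and stage splits. The proportional-hazards check is an error on its face. The primary endpoint is untouched, so this should be corrected but does not threaten the main result.

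**What to change.** In section 3.3.3, with matching wording in section 3.3.2.2:

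- **Severity:** analyse all randomised patients on a four-level ordinal outcome (no AKI, stage 1, 2, 3), and check proportional odds.
- **Persistent AKI at day 7:** report as a proportion of all randomised patients.
- **Recovery:** replace the between-arm log-rank with an all-randomised measure to day 7, such as days alive and free of AKI, with a stated rule for death. Keep recovery time among AKI cases as description only.
- **RRT duration:** describe it among recipients, or use RRT-free days over the in-hospital period with a stated rule for death and discharge. A day-30 version would go beyond the plan, which records RRT only in hospital.

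The cost is small. Daily creatinine and urine output to day 7 are already planned for every patient, so this is SAP wording plus one derived endpoint. That endpoint needs a value choice for death, and the formal test of recovery time among cases is given up.
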